# 8.4.6 SAE REPORTING

The study clinician will immediately report to the FDA any SAEs, whether or not considered study intervention related, including those listed in the protocol or investigator brochure and must include an assessment of whether there is a reasonable possibility that the study intervention caused the event. Study endpoints that are SAEs (e.g., all-cause mortality) must be reported in accordance with the protocol unless there is evidence suggesting a causal relationship between the study intervention and the event (e.g., death from anaphylaxis). In that case, the investigator must immediately report the event to the sponsor.

All SAEs will be followed until satisfactory resolution or until the site investigator deems the event to be chronic or the participant is stable. Other supporting documentation of the event may be requested by the DCC/study sponsor and should be provided as soon as possible.

It is the responsibility of the PI and the research team to ensure that SAEs are reported according to the Code of Federal Regulations, Good Clinical Practices, the protocol guidelines, the sponsor's guidelines, and IRB policy.

All adverse experience reports must include the patient number, age, sex, weight, severity of reaction (mild, moderate, severe), relationship to study drug (probably related, unknown relationship, definitely not related), date and time of administration of test medications, all concomitant medications, and medical treatment provided. The PI is responsible for evaluating all AEs to determine whether criteria for "serious" as defined above are present. Adverse drug reactions that are serious, unlisted/unexpected, and at least possibly associated to the drug, and that have not previously been reported in the IB, or reference safety information document should be reported promptly to the FDA in writing by each investigator/physician engaged in clinical research. A clear description of

the suspected reaction should be provided along with an assessment as to whether the event is drug or disease related.

# 8.4.7 REPORTING EVENTS TO PARTICIPANTS

As these medications and procedures are part of a Phase 1/2 protocol, their side effects have not been evaluated or approved for safety by the FDA. Although it is anticipated that this protocol is relatively safe, fatal complications are possible. The major hazards are infection and disease progression. It is therefore only appropriate to carry out this experimental procedure in the context of life threatening metastatic cancer. The major discomforts are nausea, mucositis, anorexia, diarrhea, fever and malaise. Physicians have an ethical responsibility to inform patients about AEs and SAEs.

Patients will be addressed by a nurse or physician to disclose AEs and SAEs. These individuals will explain the AE/SAE in an honest, open, and direct manner in a private setting. The nurse or physician will be given a detailed description of the event, incident, experience or outcome, as well as an explanation as to why it is considered an AE/SAE. They will be informed of any changes to protocol or corrective actions that will result from the AE/SAE. The physician will continue to monitor the AE/SAE in the most appropriate manner for the situation and will, if necessary, withdraw the patient from the study.

Other patients enrolled in the study will be informed of changes to protocol that are resultant of another participant's AE/SAE. They will not be given any personal details of the patient of their AE/SAE in order to protect patient privacy.

Patients will be encouraged to communicate any incidental side effects or information discovered during study procedures. Patients will be holistically monitored for signs of any unintentional or incidental effects of the study. Physicians will communicate any incidental findings that may affect the patient or the patients' desire to participate in the study.

# 8.4.8 EVENTS OF SPECIAL INTEREST

Not applicable.

#### 8.4.9 REPORTING OF PREGNANCY

Pregnancy, although not itself an SAE, should also be reported on an SAE form or pregnancy form and be followed up to determine outcome, including spontaneous or voluntary termination, details of birth, and the presence or absence of any birth defects or congenital abnormalities.

#### 8.5 UNANTICIPATED PROBLEMS

#### 8.5.1 DEFINITION OF UP

The OHRP considers UPs involving risks to participants or others to include, in general, any incident, experience, or outcome that meets all of the following criteria:

- Unexpected in terms of nature, severity, or frequency given (a) the research procedures that are described in the protocol-related documents, such as the IRB-approved research protocol and informed consent document; and (b) the characteristics of the participant population being studied;
- Related or possibly related to participation in the research ("possibly related" means there is a reasonable
  possibility that the incident, experience, or outcome may have been caused by the procedures involved in
  the research); and
- Suggests that the research places participants or others at a greater risk of harm (including physical, psychological, economic, or social harm) than was previously known or recognized.

This definition could include an unanticipated adverse device effect, any serious adverse effect on health or safety or any life-threatening problem or death caused by, or associated with, a device, if that effect, problem, or death was not previously identified in nature, severity, or degree of incidence in the investigational plan or application (including a supplementary plan or application), or any other unanticipated serious problem associated with a device that relates to the rights, safety, or welfare of subjects (21 CFR 812.3(s)).

#### 8.5.2 UNANTICIPATED PROBLEM REPORTING

The investigator will report UPs to the reviewing IRB and to the DCC/lead PI. The UP report will include the following information:

- Protocol identifying information: protocol title and number, Pl's name, and the IRB project number;
- A detailed description of the event, incident, experience, or outcome;
- An explanation of the basis for determining that the event, incident, experience, or outcome represents an UP:
- A description of any changes to the protocol or other corrective actions that have been taken or are proposed in response to the UP.

To satisfy the requirement for prompt reporting, UPs will be reported using the following timeline:

- UPs that are SAEs will be reported to the IRB, depending on their policy, and to the DCC/study sponsor within 7 working days of the investigator becoming aware of the event.
- Any other UP will be reported to the IRB and to the DCC/study sponsor within 7 working days of the investigator becoming aware of the problem.
- All UPs should be reported to appropriate institutional officials (as required by an institution's written reporting procedures), the supporting agency head (or designee), and the OHRP within 7 working days of the IRB's receipt of the report of the problem from the investigator.

An investigator shall submit to the sponsor and to the reviewing IRB a report of any unanticipated adverse device effect occurring during an investigation as soon as possible, but in no event later than 7 working days after the investigator first learns of the effect (21 CFR 812.150(a)(1)), A sponsor who conducts an evaluation of an unanticipated adverse device effect under 812.46(b) shall report the results of such evaluation to the FDA and to all reviewing IRB's and participating investigators within 7 working days after the sponsor first receives notice of the effect. Thereafter the sponsor shall submit such additional reports concerning the effect as FDA requests (21 CFR 812.150(b)(1)).

### 8.5.3 REPORTING UNANTICIPATED PROBLEMS TO PARTICIPANTS

As these medications and procedures are part of a Phase 1/2 protocol, they may cause wholly unknown and unexpected side effects. Unexpected problems will be reported to patients as soon as possible.

A nurse or physician will be given a detailed description of the event, incident, experience or outcome, as well as an explanation as to why it is considered a UP. They will be informed of any changes to protocol or corrective actions that will result from the UP.

Other patients enrolled in the study will be informed of changes to protocol that are resultant of another participant's UP. They will not be given any personal details of the patient of their UP in order to protect patient privacy.

# 9 STATISTICAL CONSIDERATIONS

#### 9.1 STATISTICAL HYPOTHESES

We hypothesize that a source of CD8+ depleted, non-engrafting, HLA-mismatched, unrelated donor lymphocyte infusion (NE-DLI) would be capable of reversing immune tolerance and eliciting a significant antitumor response in patients with MDS and secondary AML, without causing GVHD.

#### **Primary Endpoint:**

 Determine the maximum tolerated dose (MTD) of CD8depleted cells from HLA-mismatched unrelated donors infused after induction chemotherapy for patients with advanced MDS after HMA failure or untreated sAML

#### **Secondary Endpoints:**

To determine:

- Overall response rate according to the International Working Group (IWG) (see Appendix B).
- Overall survival.
- Progression-free survival.
- Hematologic response/improvement by IWG 2006 criteria for MDS patients and the IWG 2003 criteria for AML (1, 2).
- Occurrence of adverse events.
- Unexpected transplant complications (eg, graft-versus-host disease [GvHD]).

# 9.2 SAMPLE SIZE DETERMINATION

See Sections 9.4.2 and 9.4.4

#### 9.3 POPULATIONS FOR ANALYSES

Not Applicable

#### 9.4 STATISTICAL ANALYSES

#### 9.4.1 GENERAL APPROACH

This is a phase 1b/2 study with dose escalation for determination of the MTD/RP2D of NE-DLI via a traditional 3+3 dose escalation schemaa followed by an expansion cohort for assessing safety profile and preliminary estimation of the overall response rate (ORR) (complete response and partial response based on International Working Group definition). Eligible patients will be treated with NE-DLI in the pre-transplantation setting.

9.4.1.	1 ANA	ALYSIS	PLAN
--------	-------	--------	------

<sup>a See Appendix F

Toxicity events for NE-DLI will be descriptively summarized at each dose level. The response rates, including ORR and hematologic response by IWG 2006 criteria will be estimated via an exact binomial test with 95% confidence interval in combining patients treated at the RP2D dose level and the expansion cohort patients. Overall survival, defined from date of treatment to date of death or censored at last follow-up date, will be estimated via Kaplan-Meier method (combining patients treated at the RP2D dose level and expansion cohort patients). Other outcomes such as independence from red blood cell transfusion or platelet transfusion for 56 consecutive days or more, occurrence of AE, unexpected transplant complications will be descriptively reported via summary statistics.

# 9.4.2 ANALYSIS OF THE PRIMARY ENDPOINT(S)

For the dose escalation portion, a minimum of two subjects and a maximum of 18 subjects will be enrolled. There will be three dose levels in the dose escalation portion. MTD is defined as the highest dose level with the probability of DLT less than 33% (DLT events are defined in Section 6). The DLT observation window will be until confirmation that the donor cells have been rejected (ANC ≥ 500/microL AND confirmation of either bone marrow donor chimerism <5% or donor blood CD3+ chimerism <5%) OR within 56 days following NE-DLI, whichever occurs first. Per the traditional 3+3 schema, up to three patients may be enrolled concurrently and treated at the same dose level. The first three patients will be treated at dose level 1. For each dose level, if none of three patients experiences a DLT, we will escalate to the next dose level until reaching dose level 3. For each dose level, if one of the three patients experiences a DLT, we will enroll three additional patients and treat at the same dose level. In this case, if none of these additional three patients experiences a DLT, we will escalate the dosage to next level until reaching dose level 3. For each dose level, if two or more patients among six enrolled patients experience a DLT, or two or more patients in the three patient cohort experience DLT, the dosage level exceeds the MTD and the previous dose level will be declared as the MTD. If the first dose level exceeds the MTD, the study will be suspended. If no subjects experience a DLT at any dose level, the MTD will be level 3 (5 x 10^7 CD4+ T cells/kg). Similarly, if exactly one of six patients enrolled at dose level 3 experiences a DLT, then the MTD will be dose level 3. All patients in a dose level must be observed through the DLT window prior to enrolling patients at a higher dose level.

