# 1.3 SCHEDULE OF ACTIVITIES (SOA)

For explanation of procedures, please see Section 8 (Study Assessments and Procedures).

· · · · · · · · · · · · · · · · · · ·	Initial	Allowable time from start of induction	Starting Day 0	Day 28	Day 42	Day 56	6 months +/- 2 weeks	1 yr +/- 2 weeks
History and physical	Х	Within 30 days			Х	Х	X	X
Performance status	Χ	Within 30 days						
Staging Bone Marrow Biopsy and aspirate for research	Х	Within 30 days			X a			
Peripheral blood for research	Х		Daily days 0-7		X a			
CBC & Diff	x	Within 7 days	ANC<50 0- 3x/week ANC≥50 0- weekly to day 56		×	×	×	x
СМР	Х	Within 7 days	Weekly to day 56		Х	Х	Х	Х
CXR or Chest CT	Х	Within 30 days						
Pregnancy test (women, childbearing age)	Х	Within 30 days						
Human Immunodeficiency Virus	Х	Within 30 days						
EKG	Х							
MUGA or ECHO	Х	Within 30 days						
HLA typing	Χ							
Anti-donor HLA antibody testing	Χ				Χ			
Adverse Event Monitoring			Weekly to day 56		х	х	×	X
GvHD evaluation			At onset, weekly until resolves		х	х		
Peripheral blood or bone marrow for donor chimerism					Xa	Xp		
CMV IgG	Х	Within 30 days						
CMV PCR			Weekly through day 56					
C Reactive Protein	Х	Within 7 days	Weekly through day 56		_			
Ferritin	Х	Within 7 days	Weekly through day 56		х	х		

Abbreviations: ANC, absolute neutrophil count; CBC, complete blood count; CMP, comprehensive metabolic panel; CMV, cytomegalovirus; CXR, chest radiograph; CT, computerized tomography scan; diff, differential blood count; ECHO, echocardiogram; EKG, electrocardiogram; GvHD, graftversus-host disease; MUGA, multigated acquisition; PCR., polymerase chain reaction

Tracking of days begins from day of cell transfusion (eg, Day 56 is 56 days after initial cell infusion). Day of cell transfusion is marked as Day 0. Procedures can be performed  $\pm$  3 days from marked date, unless otherwise specified. aSpecified day 42 samples may be performed prior to day 42 if the patient has recovered from aplasia, defined as ANC >500/µl. Otherwise, the specimen collections will be planned for day 42 +/-3 days. b Day 56 chimerism measurement may be omitted if donor T-cell chimerism is < 5% on first measurement or if whole blood/marrow chimerism is < 5% when T-cell chimerism is not measurable. If donor chimerism >5% on day 56, then the investigator will continue performing monthly GVHD evaluations and chimerism until donor T-cell chimerism decreases to <5% or until 1 year, whichever comes first.

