# 4.3 JUSTIFICATION FOR DOSE

For the dose-escalation portion, a minimum of 2 subjects and a maximum of 18 subjects will be enrolled. There will be 3 dose levels in the dose-escalation portion. MTD is defined as the highest dose level with the probability of DLT less than 33% (DLT events are defined in Section 6). The DLT observation window will be within 56 days following NE-DLI. If none of 3 patients experience a DLT, we will escalate to the next dose level. If one of the 3 patients experiences a DLT, we will enroll 3 additional patients and treat at the same dose level. In this case, if none of these additional 3 patients experiences a DLT, we will escalate to the dosage to next level. If 2 or more patients

among 6 enrolled patients experience a DLT, or 2 or more patients in the 3 patient cohort experience DLT, the dosage level exceeds the MTD and the previous dose level will be declared as the MTD. If the first dose level exceeds the MTD, the study will be suspended. If no subjects experience a DLT at any dose level, the MTD will be level 3 ( $5 \times 10^7$  CD4+ T cells/kg).

The RP2D is defined as the dose level selected to be evaluated in the expansion cohort or future phase II studies and will be equivalent to the MTD determined in the phase 1b portion of the study. Once we determine the RP2D level, we will enroll 10 additional eligible patients and treat with the RP2D level. The goal for this expansion cohort is to evaluate the safety and tolerability for patients who will be treated with NE-DLI in the RP2D dose level, and to evaluate the preliminary efficacy estimate for the ORR. Including the dose-escalation portion in which 3 or 6 enrolled patients will have been treated at the RP2D level, a total of at least 13 patients will be treated at the RP2D level. Based on previous data, (18) the complete response rate using microtransplantation was in the range of 36%-52% for MDS or AML from antecedent MDS patients. Hence, for the phase 2 portion, an ORR of 45% is considered clinically meaningful. With a sample size of 13 patients, if our ORR is 45%, the 95% CI (exact binomial) will be (18-74%); if the ORR is 50%, the 95% CI will be (22-78%).

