# 4.4 END OF STUDY DEFINITION

The phase I portion of the study will continue until reaching the MTD to determine the RP2D. The phase II portion of the study will continue until an additional 10 patients are treated at the RP2D. The maximum total number of patients enrolled in this study will be 28 (6 per dose level plus 10 in the expansion cohort). We expect that the accrual rate will be one patient per every 5-6 weeks. With the DLI observation window (56 days after DLI), the dose-escalation portion may take up to a maximum of 2.5 - 3 years to complete and an additional 1.5 years for the expansion cohort.

A participant is considered to have completed the study if he or she has completed all phases of the study including the last visit or the last scheduled procedure shown in the SOA, Section 1.3.

The end of the study is defined as completion of the last visit or procedure shown in the SOA in the trial globally.

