### 6.1.3 DURATION OF THERAPY

Subjects are eligible for only one lymphocyte infusion. For the dose-escalation portion, a minimum of 2 subjects and a maximum of 18 subjects will be enrolled. There will be 3 dose levels in the dose-escalation portion. MTD is defined as the highest dose level with the probability of DLT less than 33% (DLT events are defined in Section 6). The DLT observation window is defined in section 9.4.2. If none of 3 patients experiences a DLT, we will escalate to the next dose level. If one of the 3 patients experiences a DLT, we will enroll 3 additional patients and treat at the same dose level. In this case, if none of these additional 3 patients experiences a DLT, we will escalate to the dosage to next level. If 2 or more patients among 6 enrolled patients experience a DLT, or 2 or more patients in the

3 patient cohort experience DLT, the dosage level exceeds the MTD and the previous dose level will be declared as the MTD. If the first dose level exceeds the MTD, the study will be suspended. If no subjects experience a DLT at any dose level, the MTD will be level 3 (5 x  $10^7$  CD4+ T cells/kg).

The RP2D is defined as the dose level selected to be evaluated in the expansion cohort or future phase II studies and will be equivalent to the MTD determined in the phase 1b portion of the study. Once we determine the RP2D level, we will enroll 10 additional eligible patients and treat with the RP2D level. The goal for this expansion cohort is to evaluate the safety and tolerability for patients who will be treated with NE-DLI in the RP2D dose level, and to evaluate the preliminary efficacy estimate for the ORR. Including the dose-escalation portion in which 3 or 6 enrolled patients will have been treated at the RP2D level, a total of at least 13 patients will be treated at the RP2D level. Based on previous data, (18) the complete response rate using microtransplantation was in the range of 36%-52% for MDS or AML from antecedent MDS patients. Hence, for the phase 2 portion, an ORR of 45% is considered clinically meaningful. With a sample size of 13 patients, if our ORR is 45%, the 95% CI (exact binomial) will be (18%-74%); if the ORR is 50%, the 95% CI will be (22%-78%).

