Ferritin	X	Within 7 days	Weekly through day 56		х	Х		

Abbreviations: ANC, absolute neutrophil count; CBC, complete blood count; CMP, comprehensive metabolic panel; CMV, cytomegalovirus; CXR, chest radiograph; CT, computerized tomography scan; diff, differential blood count; ECHO, echocardiogram; EKG, electrocardiogram; GvHD, graftversus-host disease; MUGA, multigated acquisition; PCR,, polymerase chain reaction

Tracking of days begins from day of cell transfusion (eg, Day 56 is 56 days after initial cell infusion). Day of cell transfusion is marked as Day 0. Procedures can be performed ± 3 days from marked date, unless otherwise specified. a Specified day 42 samples may be performed prior to day 42 if the patient has

recovered from aplasia, defined as ANC >500/ $\mu$ l. Otherwise, the specimen collections will be planned for day 42 +/-3 days. bDay 56 chimerism measurement may be omitted if donor T-cell chimerism is < 5% on first measurement or if whole blood/marrow chimerism is < 5%. If donor chimerism >5% on day 56, then the investigator will continue measuring monthly until it decreases to <5% or until 1 year, whichever comes first.

Pre-treatment research samples may be added on to previously collected samples (e.g., Moffitt Total Cancer Care) in lieu of collecting new samples. Screening tests obtained as standard of care prior to patient consent to this trial may be used for screening purposes if the tests fall within the allowable time window to the start of induction chemotherapy as defined in the table above.

NOTE: In certain clinical circumstances (e.g. relapsed or terminally ill patients, risk of undue harm to patients, etc.) study tests may be omitted at the physician's discretion. Additionally, tests may be rescheduled as clinically indicated.

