#### 12.6 APPENDIX F: CRITERIA FOR DOSE ESCALATION

Dose escalation will occur if 0 out of the first 3 patients experience DLTs. Rules for dose escalation are as follows:

**0/3 DLTs:** Escalate the dose (dose levels 1-2), or halt dose escalation (dose level 3).

1/3 DLTs: Study an additional 3 patients. If an additional patient experiences a DLT, halt dose escalation. If no other patient experiences DLT (that is if 1/6 patients on dose level experiences DLT), escalate the dose (dose levels 1-2) or halt dose escalation (dose level 3).

2/3 DLTs: Halt dose escalation.

The decision to escalate the dose of donor peripheral blood cells and to enroll patients to the higher dose level may not be made until one of the following has occurred:

- 1. The first 3 patients have been fully evaluated for DLTs and none has experienced a DLT.
- 2. Six patients have been fully evaluated and only 1 has experienced a DLT.

The DLT observation window continues until the first of the following:

- 1. ANC > 500/microL AND confirmation the DLI has been rejected (either bone marrow donor chimerism <5% or donor blood CD3+ chimerism <5%)
- 2. Within 56 days following NE-DLI

If neither of these conditions has been met, patients will continue to be accrued to the current dose level. In the event that 0/3 patients experience DLT, accrual to the next higher dose level may proceed even if additional patients have been treated at the lower dose level and are not yet evaluable. However, if any of those patients experience DLT, accrual to the higher dose level will be suspended until a total of 6 patients have been treated and evaluated at the lower dose level. Further accrual to the higher dose level will not resume until the DLT incidence in the lower dose level is documented to be no greater than 1/6 patients. Accrual to the higher dose level will be stopped if the incidence of DLTs in the previous level exceeds 33% (for instance, if none of the first 3 patients experiences DLT, but the next 2, who were accrued during the observation period for the first 3 patients, do).

DLTs are defined as any of the following that is at least possibly attributable to the investigational treatment:

- 1. Grade 2-4 infusion toxicity
- 2. Grade 4 organ toxicity (as defined by NCI CTCAE v 5.0), not preexisting, not due to the primary malignancy, and not due to chemotherapy or infection

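### Section 4.3 states a 56-day DLT window without the early closure that 9.4.2 and Appendix F apply, and the early-closure test accepts a marrow result when blood CD3 chimerism is 5% or more, or untested

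*Combined protocol and SAP*

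**What the plan says.** **Length of the window.** Section 4.3: "The DLT observation window will be within 56 days following NE-DLI". It has no early-closure clause. Section 4.4 builds its timeline on the same length: "With the DLI observation window (56 days after DLI"). Section 6.1.3, which otherwise repeats most of 4.3, says instead: "The DLT observation window is defined in section 9.4.2". Section 9.4.2 ends the window at the earlier of day 56 and confirmed rejection of the donor cells. Appendix F has the same structure.

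**Test for early closure.** Section 9.4.2 requires ANC recovery and "confirmation of either bone marrow donor chimerism <5% or donor blood CD3+ chimerism <5"%. Appendix F requires ANC recovery and "confirmation the DLI has been rejected (either bone marrow donor chimerism <5% or donor blood CD3+ chimerism <5"%). Either compartment is enough. Section 6.1.3.1 lets the chimerism sample be whole marrow, blood CD3 or both, so a patient may have no CD3 result.

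**Related rules.** Footnote b of the schedule in 1.3 lets the day 56 chimerism test be omitted if donor T-cell chimerism is below 5%, or "if whole blood/marrow chimerism is < 5% when T-cell chimerism is not measurable". The copy of that footnote in 8.1 drops the condition: "on first measurement or if whole blood/marrow chimerism is < 5"%. Section 8.4.3.3.1 continues GvHD monitoring until donor T-cell chimerism is below 5% or one year has passed.

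**The concern.** The primary endpoint is decided by whether single events count. If the window is described in two ways, a reader of 4.3 alone would count a DLT on day 50 in a patient whose window had closed on day 42 under 9.4.2.

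The closure test raises a second issue. Its purpose is to certify that the donor cells are gone, after which GvHD should no longer be possible. As written, it can certify rejection on a marrow result alone. The same patient can then be treated as having rejected the cells for dose escalation while still being followed for GvHD because donor T cells persist. An attributable event between closure and day 56 would be seen and reported, but would not enter the 3+3 decision.

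**Working it through.** **1. Which window governs.** Section 6.1.3 points to 9.4.2, and Appendix F, which 4.1 and 9.4.1 cite for the escalation schema, agrees with 9.4.2. The early-closure rule is therefore operative, and 4.3 is the statement out of step.

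**2. The plan's own figure that depends on window length.** Section 4.4 says escalation may take at most 2.5 to 3 years.

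- Inputs (4.4 and 9.4.2): 18 patients; one patient per 5 to 6 weeks; window 56 days = 8 weeks. Assumption: six cohorts of three, with a full wait after each.
- Formula: (18 × weeks per patient + waits × window in weeks) / 52.18.
- Six waits of 8 weeks: (90 + 48)/52.18 = 2.64 years; (108 + 48)/52.18 = 2.99 years. This reproduces the stated range.
- Three waits of 8 weeks: (90 + 24)/52.18 = 2.18; (108 + 24)/52.18 = 2.53.
- Six waits of 6 weeks (closure on day 42): (90 + 36)/52.18 = 2.41; (108 + 36)/52.18 = 2.76.

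Because 4.4 states a maximum, its match to 56 days is what a cap on the window would give as well as a fixed window. It is not evidence of a conflict.

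**3. Length of the uncounted period.** Gap = 56 − closure day. Section 8.4.3.3 puts usual ANC recovery between days 21 and 42. If samples are not taken early on recovery, footnote a in 1.3 says "the specimen collections will be planned for day 42 +/-3 days".

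| Closure day | Gap (days) | Share of 56 |
|---|---|---|
| 21 | 35 | 62.5% |
| 39 | 17 | 30.4% |
| 42 | 14 | 25.0% |
| 45 | 11 | 19.6% |

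These assume the chimerism result is available on the closure day. Turnaround of t days shortens each gap by t, and the documents give no t. Day 21 is not a floor: 6.1.2.2 puts aplasia at typically at least 3 weeks from the start of chemotherapy, which for 7+3 is day −7, so recovery near day −7 + 21 = 14 is possible. That would leave 56 − 14 = 42 days.

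**4. The closure test beside the related rules.**

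| Result | 9.4.2 and Appendix F | 1.3 footnote b | 8.4.3.3.1 |
|---|---|---|---|
| CD3 <5% | closes | day 56 test may be omitted | monitoring ends |
| Marrow <5%, CD3 ≥5% | closes | not omitted | monitoring continues |
| Marrow <5%, CD3 untested | closes | omitted only if CD3 not measurable | criterion not established |

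Hypothetical case: marrow 3% and CD3 8% on day 42 with ANC recovered. The DLT window closes. Biopsy-confirmed grade 2 acute GvHD on day 50 is an SAE and fits DLT item 4, but falls outside the window.

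**5. Which DLTs can fall in the gap.** Items 2, 3, 4 and 7 of Appendix F: grade 4 organ toxicity, unresolved grade 3 organ toxicity, grade 2-4 acute GvHD and grade 5 events. Item 5 (delayed neutrophil recovery) cannot, because early closure requires recovery. Infusion toxicity comes earlier, and 8.3.1 places CRS typically in the first 7 days.

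**6. Effect on the 3+3 decision (9.4.2).** One uncounted event changes:

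- 1/3 (enrol 3 more) to 0/3 (escalate, at levels 1 and 2);
- 2/6 (dose exceeds the MTD) to 1/6 (escalate, or MTD at level 3).

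The suspension clause in Appendix F covers additional patients who are not yet evaluable. It does not reopen a closed window.

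**The case against.** The strongest reply is that 4.3 is a stale duplicate. Section 6.1.3 names 9.4.2 as the definition, and the wording in 4.3 can even be read as an outer limit. This largely stands. A reader might infer that the primary endpoint has two competing definitions; the cross-reference does not support that. What remains is one sentence in 4.3 that omits a clause of the governing rule. A reader might also infer that 4.4 contradicts 9.4.2, but a worst-case timeline properly uses the longest window.

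On the closure test, the other side can say that choosing a compartment is a clinical judgement. Footnote b and 8.4.3.3.1 serve other purposes and do not define the DLT window, and 6.1.3.1 and the 8.1 footnote treat the compartments as alternatives. That is fair, and it is why this part is an improvement and not an error. It does not remove the inconsistency that one patient can have rejected the cells for one rule and not for the other.

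Safeguards exist. Grade 2-4 acute GvHD and any death within 56 days are SAEs, SAEs go to the FDA and the monitoring committee, and the study can be suspended. A reader might infer that late events would go unseen; they would not. There is one qualification: 1.3 schedules adverse event monitoring weekly to day 56, whereas 6.1.3.1 has weekly non-hematologic assessment only to day 42. A late event must also be at least possibly attributable to the infusion to be a DLT at all.

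**Conclusion.** Two findings hold.

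1. Section 4.3 is wrong as written: it states the primary-endpoint window without the early closure in 9.4.2, which governs. The 56 days in 4.4 can stand as the maximum window.
2. The closure test in 9.4.2 and Appendix F can be improved cheaply: it accepts marrow below 5% with CD3 at 5% or more, or untested, against the T-cell criterion used for GvHD monitoring.

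For closure in the usual recovery range the uncounted period is 14 to 35 of 56 days, less turnaround. It is tempting to read 35 days as a maximum, but the documents call that range only usual. It is also tempting to attach a rise in the probability of escalating past a toxic dose. That would need the share of DLTs falling after closure, or the frequency of discordant or CD3-untested patients, and neither is given. Confidence is high on the text; the practical effect is unquantified. DLT item 5 and the aplasia definition in 8.4.3.3.2 also leave the compartment unnamed, but neither affects early closure.

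**What to change.** - **4.3 and 4.4:** replace the window sentence in 4.3 with a reference to 9.4.2, and describe the 56 days in 4.4 as the maximum window.
- **9.4.2 and Appendix F:** allow early closure only on ANC recovery plus donor CD3 chimerism below 5%. Accept whole blood or marrow below 5% only when CD3 was tested and is not measurable. Otherwise the window runs to day 56.
- **6.1.3.1 and 8.1 footnote b:** align both with that rule, so that CD3 is always attempted and the missing condition is restored. Run the weekly toxicity assessment in 6.1.3.1 to day 56, as in the schedule.
- **Leave unchanged:** DLT item 5, the aplasia definition, and GvHD monitoring to one year.

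Patients with CD3 below 5% would still close early. The cost is protocol wording, a CD3 reading at a chimerism sample that is already scheduled, and later escalation in cohorts with discordant patients: about 11 to 17 days if sampled on days 45 to 39, and longer if sampled earlier.
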